4.6.2 Timing of Study Assessments

The Schedules of Assessments can be found in [Appendix 1](#), [Appendix 2](#), [Appendix 9](#), and [Appendix 10](#).

The first cohorts of 24 adolescents and up to approximately 30 children will follow at study start a specific Schedule of Assessments (see [Appendix 2](#)) with additional assessments until the IMC and SOC determines the final doses for each age group (see protocol Section [3.1.3.1](#)). After determination of the final doses for the cohort these subjects will continue following the Schedule of Assessments for the entire study ([Appendix 1](#)). If the dose is judged acceptable on an individual level, the subject may continue on that dose and follow the Schedule of Assessments for the entire study. During the early interim Pharmacokinetic and safety reviews the IMC and SOC may decide to stop treatment (see Section [3.1.3.1](#)).

If necessary, site visits (Week 6, Week 12, Week 18, Week 24, Week 48, Week 64, Week 76, Early Withdrawal Visit, and Follow-Up Visit) can be performed over two consecutive days. Assessments at screening can be performed at any time during the screening period. Baseline assessments can be performed up to 1 week prior to first dose (see [Appendix 1](#), [Appendix 2](#), [Appendix 9](#), and [Appendix 10](#)).

4.6.2.1 Screening and Pretreatment Assessments

Written informed consent and Assent for participation in the study must be obtained before performing any study-specific screening tests or evaluations. Informed Consent Forms and Assent Forms for enrolled subjects and for subjects who are not subsequently enrolled will be maintained at the study site.

All screening and pre-treatment assessments must be completed and reviewed to confirm that subjects meet all eligibility criteria. The Investigator will maintain a screening log to record details of all subjects screened and to confirm eligibility or record reasons for screening failure.

An Eligibility Screening Form (ESF) documenting the Investigator's assessment of each screened subject with regard to the protocol's inclusion and exclusion criteria is to be completed by the Investigator and kept at the investigational site.

Abbreviated re-screening (written informed consent, medical history, physical examination, substance use, alcohol test, fasted laboratory safety, coagulation, serology, urinalysis, inclusion/exclusion criteria) may be allowed under circumstances where the subject is screen-passed but could not be randomized within the 4-week screening window due to a study halt, logistical, personal, or technical reasons. At no time should the duration between the original screening visit and the abbreviated re-screening visit exceed 3 months. Abbreviated re-screening will only be permitted in cases where this poses no safety risk to the subject.

Screen-failed subjects can be re-screened if there is a substantial change in the subject's general condition (e.g., prohibited medication was stopped or weight loss) and if recruitment for the study is still ongoing. Re-screening will not be allowed if the subject failed earlier to meet the disease specific inclusion criteria (e.g., SRS-2 T-score).

Safety laboratory tests which would exclude the subject at screening may be repeated once (as unscheduled labs) if it is suspected that the abnormal result is transient and likely to be normal at repeat.

Subjects from first adolescent and first children cohorts, who stopped treatment in the context of the interim safety and PK decisions, (see Section 3.1.3) will be allowed to re-start in the same treatment arm, according to their original randomization, for 24 weeks in the main study, provided the Investigator can exclude relevant changes in the subject's general condition (see Section 4.2.1). These subjects will have a new, abbreviated Baseline visit, and will continue with all subsequent visits according to the schedule of assessments until completion of their time on the study (Appendix 1).

In addition, re-starting subjects will be assigned a new subject number. Some data from their original screening visit will be required to be re-entered in the eCRF under the new subject number.

A screening examination will be performed approximately 4 weeks (at least 3 weeks and up to 4 weeks) before the first drug administration (Day 1) per the Schedule of Assessments, (see Appendix 1). Subjects must fulfill all entry criteria to be accepted into the study.

For subjects enrolling in first adolescent/first children cohorts (see Section 3.1 and Section 3.1.3.1), a screening examination will be performed approximately 4 weeks (at least 1 week and up to 4 weeks) before the first drug administration (Day 1) per the Schedule of Assessments (Appendix 2).

The Investigator, or designee, will use the eCRF with the assigned subject number and enter the corresponding number for allocation to the treatment group in the appropriate place on each subject's eCRF.

The randomization numbers are to be allocated sequentially in the order in which the subjects are enrolled. A Subject Enrollment and Identification Code List must be maintained by the Investigator.

4.6.2.2 Assessments during Treatment

All assessments must be performed as per Schedule of assessments (see Appendix 1, Appendix 2, Appendix 9, and Appendix 10).

Subjects will arrive at each study visit without having taken their daily dose of study medication. Following collection of the pre-dose PK blood sample, and the safety labs

subjects will take their next dose of study medication. Site staff will record the actual date and time of the dose intake. The last dose of study medication will be administered at the Week 76 visit.

When blood samples are scheduled for the same nominal time as other assessments the following order should be followed:

- 12-lead ECGs
- Vital signs
- Blood samples

As a general rule, the test sequence for all disease specific assessments should remain the same for a given subject as established at screening and Baseline. Additionally, testing should occur around the same time of the day at each visit.

For the informant based assessments the following order will be followed:

- Always the Vineland™-II will be the first informant based assessment with the caregiver.
- For all other informant based assessments there is no restriction in the order, however a sequence established at screening and Baseline should remain the same for a given subject.

The patient reported outcome measures can be performed in parallel with the informant based assessments. The following sequence is proposed: first the C-SSRS followed by the PedsQL. Ideally these assessments should be performed before administration of study medication or within 1 hour after administration.

The remaining clinician-completed measures will be completed after all other disease specific assessment to minimize any possible bias on caregiver reported assessments.

4.6.2.3 Assessments at Study Completion/Early Withdrawal Visit

Subjects who complete the study treatment period (defined as completion of 24 weeks of study treatment) or discontinue from the study early, will perform with the caregiver all assessments for the Week 24 or the Early Withdrawal visit with the caregiver, as per the schedule of assessments (see [Appendix 1](#) and [Appendix 10](#)).

4.6.2.4 Follow-Up Assessments

As per the schedule of assessments, all subjects will have safety hematology/CPK blood samples taken 2 weeks after last dose and a clinic visit 6 weeks after last dose (see [Appendix 1](#) or [Appendix 10](#)). After the study completion/Early Withdrawal visit, adverse events should be followed as outlined in Sections [5.5](#) and [5.6](#).

4.7 SUBJECT, STUDY, AND SITE DISCONTINUATION

4.7.1 Subject Discontinuation

The Investigator has the right to discontinue a subject from balovaptan or withdraw a subject from the study at any time. In addition, subjects have the right to voluntarily discontinue study drug or withdraw from the study at any time for any reason. Reasons for discontinuation of study drug or withdrawal from the study may include, but are not limited to, the following:

- Subject withdrawal of consent at any time
- Any medical condition that the Investigator or Sponsor determines may jeopardize the subject's safety if he or she continues in the study
- Investigator or Sponsor determines it is in the best interest of the subject
- Subject non-compliance

4.7.1.1 Discontinuation from Study Drug

The Investigator must diligently review incoming safety data. In particular hematological or neurological abnormalities should be considered as a potential reason to withdraw a patient from further trial participation.

Subjects must be discontinued from study drug in case of:

- [REDACTED]
- [REDACTED]
- [REDACTED]

- Subject unable to continue to comply with study requirements

Subjects who discontinue study drug prematurely will be asked to return to the clinic for a study completion/Early Withdrawal visit as soon as possible (see Section 4.6.2.3) including detailed safety and efficacy assessments (see Schedule of Assessments, Appendix 1 and Appendix 2) and may undergo follow-up assessments (see Section 4.6.2.4). The primary reason for premature study drug discontinuation should be documented on the appropriate eCRF.

4.7.1.2 Withdrawal from Study

Every effort should be made to obtain information on subjects who withdraw from the study. The primary reason for withdrawal from the study should be 5.1.3 documented on the appropriate eCRF.

Subjects will not be followed for any reason after full consent has been withdrawn.

When a subject voluntarily withdraws from the study, or is withdrawn by the Investigator, samples collected until the date of withdrawal will be analyzed, unless the subject specifically requests for these to be discarded, or local laws require their immediate

destruction. A subject's withdrawal from Study BP30153 does not, by itself, constitute withdrawal of specimens donated to the Research Biosample Repository.

4.7.2 Study and Site Discontinuation

The Sponsor has the right to terminate this study at any time. Reasons for terminating the study may include, but are not limited to, the following:

- The incidence or severity of adverse events in this or other studies indicates a potential health hazard to subjects
- Subject enrollment is unsatisfactory
- Three or more subjects (delta between active and placebo arm) are pre-maturely withdrawn from the study because of serious adverse events or adverse events of special interest that are of similar nature and considered related to the intake of balovaptan (see also [Appendix 3](#)).

The Sponsor will notify the Investigator and Health Authorities if the study is placed on hold, or if the Sponsor decides to discontinue the study or development program.

The Sponsor has the right to close or replace a site at any time. Reasons for replacing or closing a site may include, but are not limited to, the following:

- Excessively slow recruitment
- Poor protocol adherence
- Inaccurate or incomplete data recording
- Non-compliance with the International Council for Harmonisation (ICH) guideline for Good Clinical Practice

5. ASSESSMENT OF SAFETY

5.1 SAFETY PARAMETERS AND DEFINITIONS

Safety assessments will consist of monitoring and recording adverse events, including serious adverse events, and non-serious adverse events of special interest; measurement of protocol-specified safety laboratory assessments; measurement of protocol-specified vital signs, ECGs; and other protocol-specified tests that are deemed critical to the safety evaluation of the study.

Certain types of events require immediate reporting to the Sponsor, as outlined in Section [5.4](#).

5.1.1 Adverse Events

According to the ICH guideline for Good Clinical Practice, an adverse event is any untoward medical occurrence in a clinical investigation subject administered a pharmaceutical product, regardless of causal attribution. An adverse event can therefore be any of the following:

- Any unfavorable and unintended sign (including an abnormal laboratory finding), symptom, or disease temporally associated with the use of a medicinal product, whether or not considered related to the medicinal product.
- Any new disease or exacerbation of an existing disease (a worsening in the character, frequency, or severity of a known condition), except as described in Section [5.3.5.8](#).
- Recurrence of an intermittent medical condition (e.g., headache) not present at baseline.
- Any deterioration in a laboratory value or other clinical test (e.g., ECG, X-ray) that is associated with symptoms or leads to a change in study treatment or concomitant treatment or discontinuation from study drug.
- Adverse events that are related to a protocol-mandated intervention, including those that occur prior to assignment of study treatment (e.g., screening invasive procedures such as biopsies).

5.1.2 Serious Adverse Events (Immediately Reportable to the Sponsor)

A serious adverse event is any adverse event that meets any of the following criteria:

- Fatal (i.e., the adverse event actually causes or leads to death)
- Life threatening (i.e., the adverse event, in the view of the Investigator, places the subject at immediate risk of death).
This does not include any adverse event that had it occurred in a more severe form, or was allowed to continue, might have caused death.
- Requires or prolongs inpatient hospitalization (see Section [5.3.5.9](#))
- Results in persistent or significant disability/incapacity (i.e., the adverse event results in substantial disruption of the subject's ability to conduct normal life functions)
- Congenital anomaly/birth defect in a neonate/infant born to a mother exposed to study drug
- Significant medical event in the Investigator's judgment (e.g., may jeopardize the subject or may require medical/surgical intervention to prevent one of the outcomes listed above)

The terms "severe" and "serious" are not synonymous. Severity refers to the intensity of an adverse event (rated as mild, moderate, or severe (see Section [5.3.3](#)); the event itself may be of relatively minor medical significance (such as severe headache without any further findings).

Severity and seriousness need to be independently assessed for each adverse event recorded on the eCRF.

Serious adverse events are required to be reported by the Investigator to the Sponsor immediately (i.e., no more than 24 hours after learning of the event; see Section 5.4.2 for reporting instructions).

5.1.3 Non-Serious Adverse Events of Special Interest (Immediately Reportable to the Sponsor)

Non-serious adverse events of special interest are required to be reported by the Investigator to the Sponsor immediately (i.e., no more than 24 hours after learning of the event; see Section 5.4.2 for reporting instructions). Adverse events of special interest for this study include the following:

█ [REDACTED]

█ [REDACTED]

█ [REDACTED]

█ [REDACTED]

- Cases of an elevated ALT or AST in combination with either an elevated bilirubin or clinical jaundice, as defined in Section 5.3.5.6
- Suspected transmission of an infectious agent by the study drug, as defined below:
 - Any organism, virus, or infectious particle (e.g., prion protein transmitting transmissible spongiform encephalopathy), pathogenic or non-pathogenic, is considered an infectious agent. A transmission of an infectious agent may be suspected from clinical symptoms or laboratory findings that indicate an infection in a patient exposed to a medicinal product.
This term applies only when a contamination of the study drug is suspected.

5.2 SAFETY PLAN

█ [REDACTED]

[Redacted]

[Redacted]

[Redacted]

[Redacted]

[Redacted]

[Redacted]

[Redacted]

[Redacted]

[Redacted]

[Redacted]

[Redacted]

[REDACTED]

[REDACTED]

[REDACTED]

[REDACTED]

5.2.2 Blood Pressure and ECG Monitoring

While the overview of available respective clinical experience does not indicate an effect of balovaptan on heart rate and blood pressure, hypothetically antagonism of V1a could result in a decrease in blood pressure and impairment of orthostatic function.

- Blood pressure and pulse rate in supine position and in context of orthostatic challenge testing will be monitored in this study in pediatric patients.

As a standard policy of clinical trials sponsored by Roche, and not because of any specific concern of balovaptan, the following stopping rule is implemented with respect to QTc:

- A confirmed value for QTcF above 500 ms or a change from baseline by more than 60 ms will result in drug discontinuation (to confirm the initial abnormal value the ECG should be repeated within 30 minutes).

[REDACTED]

[REDACTED]

[REDACTED]

[REDACTED]

[REDACTED]

[REDACTED]

[REDACTED]

[REDACTED]

[REDACTED]

[REDACTED]

[REDACTED]

[REDACTED]

[REDACTED]

[REDACTED]

[REDACTED]

[REDACTED]

[REDACTED]

[REDACTED]

[REDACTED]

[REDACTED]

[REDACTED]

[REDACTED]	[REDACTED]
[REDACTED]	[REDACTED]
[REDACTED]	[REDACTED]
[REDACTED]	[REDACTED]
[REDACTED]	[REDACTED]
[REDACTED]	[REDACTED]
[REDACTED]	[REDACTED]

[REDACTED]

[REDACTED]

[REDACTED]

5.2.6 Tanner Staging

Animal studies do not point to any adverse effects of balovaptan with respect to sexual maturation. As a matter of routine monitoring, Tanner stages will be determined in subjects aged at least 7 years, but no longer after menarche in female and no longer after voice break in male subjects, and based upon agreement/approval by the site Principle Investigator, legally authorized representative, patient, and IRB as outlined in [Appendix 6](#).

5.3 METHODS AND TIMING FOR CAPTURING AND ASSESSING SAFETY PARAMETERS

The Investigator is responsible for ensuring that all adverse events (see Section [5.1.1](#) for definition) are recorded on the Adverse Event eCRF and reported to the Sponsor in accordance with instructions provided in this section and in Sections [5.4](#) to [5.6](#). For each adverse event recorded on the Adverse Event eCRF, the Investigator will make an assessment of seriousness (see Section [5.1.2](#) for seriousness criteria), severity (see Section [5.3.3](#)), and causality (see Section [5.3.4](#)).

5.3.1 Adverse Event Reporting Period

Investigators will seek information on adverse events at each subject contact. All adverse events, whether reported by the subject or noted by study personnel, will be recorded in the subject's medical record. Adverse events will then be reported on the Adverse Event eCRF as follows:

After informed consent has been obtained **but prior to initiation of study drug**, only serious adverse events caused by a protocol-mandated intervention should be reported (e.g., serious adverse events related to invasive procedures such as biopsies). Any other adverse event should not be reported.

After initiation of study drug, all adverse events, regardless of relationship to study drug, will be reported until 6 weeks after the last dose of study drug.

After a period of 6 weeks from the last dose of study drug, Investigators should only report any deaths, serious adverse events, or other adverse events of concern that are believed to be related to prior treatment with study drug (see Section [5.6](#)).

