3.1.1 Overview of Study Design

The total duration of the study (from screening through to study completion) for each subject will be approximately 87 weeks divided as follows:

[figure not shown]
- Screening period (first adolescent/children cohorts): Approximately 4 weeks
 - at least 1 week and up to 4 weeks prior to randomization
- Screening period (main study): Approximately 4 weeks
 - at least 1 week and up to 4 weeks prior to randomization
- Treatment phase*: 24 weeks
- Optional OLE: Approximately 52 weeks
- Follow-up: At least 6 weeks and up to 7 weeks after last dose

* A small group of subjects may receive blinded treatment for up to 32 weeks. These are subjects from the first PK cohort who stopped treatment prior to determination of final doses by the IMC and SOC, and have the opportunity to re-start in the main study (see protocol Section 3.1.3.1).

Approximately 340 children and adolescents aged 5–17 years with ASD will be recruited to ensure a total of 160 evaluable subjects *with placebo or 10 mg eq after 24 weeks of treatment (see Figure 1 and Figure 2)*. All individuals who received doses of balovaptan that were not equivalent to 4 mg or 10 mg will not be included in the primary analysis.

[figure not shown]
Randomization will be stratified by age group and sex. The ratio between adolescents (aged 13–17 years) and children (aged 5–12 years) will be approximately 1:1. The children’s cohort should contain up to approximately 30 subjects of whom up to approximately 16 should be aged between 5 and 7 years old. Additionally, the proportion of female subjects will be balanced in each treatment group and limited to a maximum of 20% of the entire study population.

Figure 1 Study Design for Subjects Enrolled prior to Version 6

Subjects will be randomized in a ratio of 1:1:1 and receive doses providing an exposure approximately equivalent to the 4 mg/day and 10 mg/day or placebo exposures observed in adults (see [Table 1](#) for predicted doses). Age-adjusted doses were derived using a physiologically-based pharmacokinetic (PBPK) model.

Figure 2 Study Design for Subjects Enrolled in Accordance to Version 6

eq = equivalent.

Subjects will be randomized in a ratio of 1:1 and receive doses equivalent to the 10 mg/day or placebo exposures observed in adults (see [Table 2](#) for predicted doses).

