4.6.1.2 Physical and Neurological Examinations

At the time-points listed in the Schedule of Assessments ([Appendix 1](#), [Appendix 2](#), [Appendix 9](#), and [Appendix 10](#)) a complete physical examination will be performed at screening and Week 24 or early withdrawal visit and will include an evaluation of the head, eyes, ears, nose, throat, neck, and lymph nodes and the cardiovascular, dermatological, musculoskeletal, respiratory, gastrointestinal, and neurological systems. At other clinic visits listed in [Appendix 1](#), [Appendix 2](#), [Appendix 9](#), and [Appendix 10](#) or as clinically indicated, limited, symptom-directed physical examinations should be performed. Changes from baseline abnormalities should be recorded in subject's notes. The physical exam will not include pelvic, rectal, or breast exams.

At all time-points listed in the Schedule of Assessments ([Appendix 1](#), [Appendix 2](#), [Appendix 9](#), and [Appendix 10](#)), a complete and neurological examination including an examination for symptoms of peripheral neuropathy will be performed, see [Appendix 5](#) and Section [5.2.3](#)).

Any abnormality identified at screening should be recorded on the General Medical History and Baseline Conditions eCRF section and carefully evaluated in terms of eligibility of subject for enrollment into this study.

Body height and weight will be recorded as specified in [Appendix 1](#), [Appendix 2](#), [Appendix 9](#), and [Appendix 10](#). Body Mass Index (BMI) including age and sex specific BMI Percentiles relevant for inclusion will be derived at screening. These anthropometric parameters will be determined according to <https://nccd.cdc.gov/dnpabmi/Calculator.aspx>. Screenshots of this derivation will be kept in the source data.

Results from these examinations will be documented in the eCRF forms and new or worsened clinically significant abnormalities should be recorded as adverse events on the Adverse Event eCRF.

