5.6 POST-STUDY ADVERSE EVENTS

The Investigator is not required to actively monitor subjects for adverse events after the end of the adverse event reporting period (defined as 6 weeks after the last dose of study drug). However, the Sponsor should be notified if the Investigator becomes aware of any death or any other serious adverse event occurring after the end of the adverse event reporting period, if the event is believed to be related to prior study drug treatment.

The Investigator should report these events directly to the Sponsor or its designee, either by faxing or by scanning and emailing the Serious Adverse Event/Adverse Event of Special Interest Reporting Form using the fax number or email address provided to Investigators (see "Protocol Administrative and Contact Information & List of Investigators").

5.7 EXPEDITED REPORTING TO HEALTH AUTHORITIES, INVESTIGATORS, INSTITUTIONAL REVIEW BOARDS, AND ETHICS COMMITTEES

The Sponsor will promptly evaluate all serious adverse events and non-serious adverse events of special interest against cumulative product experience to identify and expeditiously communicate possible new safety findings to Investigators, IRBs, and applicable health authorities based on applicable legislation.

To determine reporting requirements for single adverse event cases, the Sponsor will assess the expectedness of these events to balovaptan, which is the only IMP studied in this trial, using the following reference document as "Reference Safety Information":

- Section 6.4 of the IB. [45]

Independent from the causality assessment, the following SAEs and non-serious AESIs will be reported to FDA on an expedited basis:

Death, arrhythmia, syncope, dyspnea, palpitations, and chest pain

The Sponsor will compare the severity of each event and the cumulative event frequency reported for the study with the severity and frequency reported in the applicable reference document.

Reporting requirements will also be based on the Investigator's assessment of causality and seriousness, with allowance for upgrading by the Sponsor as needed.

The IMC and the independent SOC will monitor the incidence of these expected events during the study. An aggregate report of any clinically relevant imbalances that do not favor the test product will be submitted to health authorities.

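### The final double-blind safety visit, held within its permitted window, can fall up to 7 days after all-adverse-event reporting has stopped

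*Protocol*

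**What the plan says.** **Reporting period.** Protocol Section 5.3.1: after the first dose, "all adverse events, regardless of relationship to study drug, will be reported until 6 weeks after the last dose of study drug". After that limit, "Investigators should only report any deaths, serious adverse events, or other adverse events of concern that are believed to be related to prior treatment". Section 5.6 gives the same 6-week definition and does not require active monitoring afterwards. It asks the investigator to notify the sponsor only of a death or "any other serious adverse event occurring after the end of the adverse event reporting period", and only if the event is thought related.

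**Last visit.** Section 3.1.1: "Follow-up: At least 6 weeks and up to 7 weeks after last dose". Appendix 1 puts the Week 24 visit at Day 169 and the 6-week follow-up at Day 211, with a one-sided window of +7 days. Appendix 2 has the same pattern (day 42, +7) for first-cohort subjects who stop treatment.

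**What is done there.** The Appendix 1 visit includes physical and neurological examination, vital signs, ECG, haematology, full chemistry and C-SSRS. Section 5.3.1 also has investigators ask about adverse events at every contact.

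**What should be recorded.** Section 4.6.1.2, without a time limit: "new or worsened clinically significant abnormalities should be recorded as adverse events on the Adverse Event eCRF". Sections 5.3.5.4 and 5.3.5.5 treat clinically significant laboratory and vital-sign results in the same way.

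No section extends the reporting period to the actual visit date, or says outright whether the limit refers to onset, detection or report date.

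**The concern.** For a subject who completes Week 24 and does not enter the extension, this is the only full safety examination off drug. The 2-week follow-up has only blood samples and safety questions. The reporting period closes on the first day on which the full visit may take place.

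Suppose an abnormal ECG, blood count or neurological sign is first seen at a visit on day 45. Sections 4.6.1.2, 5.3.5.4 and 5.3.5.5 point to an adverse-event record. Section 5.3.1 points away from one unless the investigator believes the finding is related and of concern. The same finding on day 42 would be recorded without a relatedness judgement. Whether it reaches the adverse-event tables then depends on the visit day and on a causality opinion.

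Sites also have two rules for that week. Section 5.3.1 keeps related non-serious events of concern; Section 5.6 names only deaths and serious events.

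**Working it through.** **Inputs**

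| Item | Value | Source |
|---|---|---|
| End of all-adverse-event reporting | 6 weeks = 42 days after last dose | Protocol 5.3.1, 5.6 |
| Week 24 visit, last double-blind dose | Day 169 (window ±2) | Appendix 1 |
| 2-week follow-up | Day 183 (window ±2) | Appendix 1 |
| 6-week follow-up | Day 211 (window +7) | Appendix 1 |
| Extension: last dose; visit labelled 6-week follow-up | Week 76; Week 88 | Section 4.6.2.2; Appendix 10 |

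**Step 1: reproduce the plan's visit timing.** 211 − 169 = 42 days = 6 weeks. 211 + 7 − 169 = 49 days = 7 weeks. This matches Section 3.1.1. The plan's totals also use 7 weeks of follow-up: 24 + 7 = 31 and 24 + 52 + 7 = 83 weeks (Section 3.2), and 4 + 24 + 52 + 7 = 87 weeks (Section 3.1.1).

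**Step 2: compare the window with the limit.** Permitted visit days are 42 to 49, which is 8 days. Day 42, the nominal day, lies on the limit. The other 7 lie 1 to 7 days past it. This counts permitted days and does not forecast when visits happen.

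**Step 3: how much of the history taken at the visit is lost if the limit means onset.** Take the look-back from the 2-week contact (183 − 169 = day 14) to a visit on day v. The share inside the reporting period is (min(v, 42) − 14) / (v − 14):

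- v = 42: 28/28 = 100%
- v = 45: 28/31 = 90%
- v = 49: 28/35 = 80%

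If the 2-week contact moves by ±2 days, the day-49 figure is 30/37 = 81% or 26/33 = 79%. So at most about one fifth of the look-back lies outside, all of it on days 43 to 49.

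**Step 4: what is not reportable on days 43 to 49.** Under Section 5.3.1, related deaths, related serious events and related events of concern stay reportable. What drops out is (a) non-serious events judged unrelated or not of concern and (b) unrelated serious events. Onset decides this for events elicited by history. For a laboratory, ECG or examination abnormality with no known earlier start, the date of first detection decides, and that is the visit day.

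**Step 5: extension subjects.** Appendix 10 labels Week 88 as the 6-week follow-up, but 88 − 76 = 12 weeks. That conflicts with the 6 to 7 weeks in Section 3.1.1 and the 83 weeks in Section 3.2, so Steps 1 to 4 cannot be carried over until those passages agree.

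**The case against.** A reader might infer that most findings at the last visit fall outside the reporting period, since 7 of 8 permitted days are past the limit. The documents do not support that. The nominal visit is on day 42 and no distribution of visit dates is given. Section 5.6 describes post-period events by when they occur, which suggests an onset rule, and on that rule 80% to 100% of the look-back is inside the period. Nor is the visit strictly never earlier than day 42. If a site counts from Day 211 and the last dose was on Day 171, the visit falls 211 − 171 = 40 days after it, although Section 3.1.1 requires at least 6 weeks.

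A reader might also infer that safety data are lost or that the comparison between arms is biased. Neither is shown. Protocol Section 6.5 and SAP Section 4.6 list and summarise laboratory values, ECG, vital signs, examinations and C-SSRS whether or not an adverse event is recorded. Section 5.3.1 sends all adverse events to the medical record, and the rule is the same in both blinded arms.

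A third tempting reading is that Section 5.7 is broken, because it promises that "Independent from the causality assessment, the following SAEs and non-serious AESIs will be reported to FDA on an expedited basis". That section governs the sponsor's onward reporting and does not set the site's collection period.

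Section 4.6.1.2 can be read as the specific instruction that captures examination findings at this visit anyway. That is a fair reading, but Section 5.3 makes reporting follow Sections 5.4 to 5.6, and sites should not have to choose.

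Finally, a fixed 6-week period gives every subject equal observation time, which ending at the visit gives up. This is a real cost, but a small one: at most 7 days on the 210 from Day 1 to Day 211, or 7/210 = 3.3%.

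What stands after all this is the mismatch itself, the missing statement on onset or detection, and the difference between Sections 5.3.1 and 5.6.

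**Conclusion.** The point holds in a limited form. A double-blind follow-up visit within its window can fall 1 to 7 days after all-adverse-event reporting has ended. Events that start or are first detected on days 43 to 49 are then left out of adverse-event reporting if they are non-serious and judged unrelated or not of concern, or serious and judged unrelated. The consequence is confined to adverse-event tabulation for that week. It does not touch the primary analysis or the separate summaries of laboratory, ECG and examination data.

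This rests on three assumptions. Visit timing is counted from the last dose, as in Section 3.1.1. Events with onset by day 42 stay reportable, which the wording of Section 5.6 suggests but does not state. And Sections 5.3.1 and 5.6 govern unrelated serious events after day 42: Section 5.4 requires serious events to be reported regardless of relationship and refers to Section 5.4.2, whose detailed text I could not see. The size of the loss in events cannot be estimated, because the documents give neither visit dates nor event rates. It is a cheap improvement rather than a serious flaw.

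**What to change.** In Sections 5.3.1 and 5.6:

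1. End the reporting period at the 6-week follow-up visit, which may be up to 7 weeks after the last dose, or at 6 weeks after the last dose if that visit is not held.
2. State that the limit applies to onset or first detection, so that an abnormality found at the visit is reportable regardless of relationship.
3. Use the same wording in both sections for what remains reportable afterwards. At present only Section 5.3.1 includes related non-serious events of concern.

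All 8 permitted visit days then fall inside the period, against the single boundary day now, and the tension with Section 4.6.1.2 disappears. The cost is a sentence or two in each section and up to 7 more days of reporting per subject, with no new visit or procedure. Observation time becomes slightly unequal; a table that needs equal follow-up can be restricted to events with onset by day 42.

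Separately, reconcile the Week 88 label in Appendix 10 with Sections 3.1.1 and 3.2 before applying the rule to extension subjects.
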